Data gathering. We will station 2 RAs in the emergency units of recruited hospitals to observe EHSP practices regarding initial care of the injured. To adequately capture EHSP practices across the entire work day, RAs will be stationed at each hospital's emergency unit in rotating 8-hour shifts. In the period before TIF introduction, RAs will use an observation form (derived from the TIF) to record the implementation (or lack thereof) of KPIs as they observe EHSPs assess and manage each injured patient. They will fill the form without interaction with EHSP or the patient. For any components of the assessment and management that they are unable to directly observe, they will obtain information from the patient records to complete the observation form before the patient leaves the emergency unit.

Additional data from medical records. They will complete the observation form with information from patient records (in the period before TIF introduction) and/or from the EHSP-filled TIF (during TIF use). Both before and after introduction of the TIF, RAs will review the medical records of all patients observed for additional details (as above) and for additional safety-related data, including occurrence of complications (e.g. infections) or death.

Methods for introducing the TIF. We will employ a stepped-wedge design in sequentially introducing the TIF to the 8 selected hospitals. We will consider two nearby hospitals as a group, thereby getting four groups of hospitals. First, following 14 weeks of initial observation of EHSP practices at all 8 selected hospitals, we will conduct a training workshop for EHSPs of the first randomly-selected group of hospitals on use of the TIF. Following the workshop, the EHSPs will be encouraged to begin use of the TIF at their hospitals. After another 14 weeks, we will conduct the training workshop for the next group of randomly selected hospitals, after which use of the TIF will begin at those hospitals. We will continue this sequential conduct of training workshops followed by use of TIF every 14 weeks until all 8 hospitals have been exhausted. The RAs will continue to observe EHSP practices for a further 14 weeks during which the TIF will be in use at all 8 hospitals. The total duration of observation of EHSP practices will be 70 weeks.

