Data management and quality control. Data will be sent from the hospital sites to the Open Data Kit cloud repository, which employs end-to-end encryption and strict user credentials to ensure data security. A data manager will review new data from each site daily for the first week of data collection, then weekly during the first month and then monthly for the entire duration of the study. Additionally, the PI will engage the coordinator at each hospital by monthly phone calls for the first 9 months, and every 2 months for the next 9 months, to discuss study progress and address any concerns.

Sample size calculations

Statistical design and power.

Specific aim 1: We expect to enroll 25 patients per site per month and so, over the 17.5 months recruitment period at the 8 sites, a total of 3,500 patients. Assuming an alpha of 0.05 and the likely baseline values (Pre-

TIF) in Table 1, we have 80% power to detect (at a minimum) the post-TIF values indicated. We consider a range of coefficients of variation. Examples of several KPIs are shown for all injured patients and for a subset of seriously injured (referred or admitted ≥ 24 hours) patients, for whom additional KPIs apply. Based on pilot data, we anticipate 40% (n=1,400) of patients will be seriously injured.

Table 1. Sample size considerations

	Percent of patients		
	Pre-TIF	Post-TIF	Range
For all injured patients			
Blood pressure recorded on arrival	70*	77.6	77.4-77.6
Heart rate recorded on arrival	60*	68.2	67.9-68.2
Consciousness level checked on arrival	50*	58.5	58.1-58.6
For seriously injured patients (referred out or admitted ≥ 24 hours)			
Chest auscultated	85**	93.4	93.3-93.5
Internal bleeding ruled out by clinical exam, US, CT, DPL, or X-Ray	27**	39.0	38.0-39.5
Distal pulses in all 4 extremities examined	54**	67.1	66.7-67.3

Post-TIF values based on mid-range coefficient of variation (COV) of 0.25. Range is for COV of 0.15 to 0.40; *Baseline values from consensus of PI and investigators from multiple Ghanaian hospitals; **Baseline values from TCC study (3). US – Ultrasonogram, CT – Computer Tomography, DPL – Diagnostic Peritoneal Lavage

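### As defined, the seriously injured subset leaves out unreferred patients who die in the emergency unit or before 24 hours, so they drop out of the serious-injury KPI analysis

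*Combined protocol and SAP*

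**What the plan says.** The rule appears twice, both times in the sample size material. The text for Specific aim 1 refers to a "subset of seriously injured (referred or admitted ≥ 24 hours) patients, for whom additional KPIs apply". The second block of Table 1 is headed "For seriously injured patients (referred out or admitted ≥ 24 hours") and lists chest auscultation, ruling out internal bleeding, and distal pulses in all four extremities. On size, the same section says "we anticipate 40% (n=1,400) of patients will be seriously injured".

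The data collection sections carry no such restriction. Under Data gathering, research assistants record KPI performance for every injured patient while care is being given. Under Additional data from medical records, they review the records of all observed patients for safety data, "including occurrence of complications (e.g. infections) or death".

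Statistical Analyses for Specific Aims 1 and 2 creates one binary variable per KPI. It names no subset or denominator for the serious-injury KPIs and does not mention early deaths.

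**The concern.** Aim 1 asks whether the TIF reduces missed steps in the initial care of the injured. A patient who bleeds to death two hours after arrival is a central case for ruling out internal bleeding. Unless referred, that patient meets neither limb of the rule and is not counted as seriously injured.

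Subset membership is also settled after the care being measured. The KPIs concern initial assessment; whether a patient counts depends on later survival and disposition. Early deaths are lost in both phases even if the TIF changes nobody's course. If the TIF did change early survival, referral or length of stay, the subsets before and after introduction would differ in case mix.

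At stake is whom the serious-injury KPI rates describe. Analysing by intention to treat does not bring back patients whom the subset definition has removed.

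**Working it through.** **1. The plan's counts.** The section says "We expect to enroll 25 patients per site per month". With 8 sites and 17.5 months, 25 × 8 × 17.5 = 3,500, and 0.40 × 3,500 = 1,400. Both reproduce. Over 8 hospitals × 5 periods = 40 hospital-periods, 1,400 / 40 = 35 seriously injured patients per hospital-period.

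**2. The plan's detectable values.** Inputs: "Assuming an alpha of 0.05" (taken as two-sided, since the plan does not say), 80% power, and "Post-TIF values based on mid-range coefficient of variation (COV) of 0.25". The Hussey-Hughes stepped-wedge variance is

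Var = I·s²(s² + T·t²) / [(I·U − W)s² + (U² + I·T·U − T·W − I·V)t²]

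Here I = 8 hospitals and T = 5 periods. U = 20 is the number of hospital-periods with the TIF, W = 120 the sum of squared period totals, and V = 60 the sum of squared hospital totals. This reduces to 8s²(s² + 5t²) / (40s² + 120t²), with s² = p̄(1 − p̄)/35, p̄ the mean of the pre and post proportions, and t = COV × baseline.

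Worked row, internal bleeding (27% to 39.0%):
- s² = 0.33 × 0.67 / 35 = 0.00632
- t² = (0.25 × 0.27)² = 0.00456
- Var = 0.00184, SE = 0.0429
- 0.12 / 0.0429 − 1.96 = 0.84, so power is 0.799

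Solving for 80% power gives 93.44, 39.02 and 67.06, against the stated 93.4, 39.0 and 67.1. One-sided alpha gives 92.6, 37.6 and 65.6, which does not fit. Table 1 is sound for the subset as defined.

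**3. The rule applied to each course.**

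| Course | Referred out | Admitted 24 h or more | In subset |
|---|---|---|---|
| Dies in the emergency unit, not referred | no | no | no |
| Admitted, dies at 10 hours, not referred | no | no | no |
| Referred out, dies within 24 hours | yes | no | yes |
| Admitted, dies after 24 hours | no | yes | yes |

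Only the first two rows are lost.

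**4. Number left out.** The documents give no early mortality, so 0.5% to 3% of all patients is an assumption.
- 0.5%: 3,500 × 0.005 = 17.5, about 18; 17.5 / 1,400 = 1.3%
- 3%: 3,500 × 0.03 = 105; 105 / 1,400 = 7.5%

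**5. Effect on power.** Adding these patients, spread evenly over the 40 hospital-periods, and solving again at COV 0.25:

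| Early deaths | Subset | Detectable post-TIF values |
|---|---|---|
| none added | 1,400 | 93.44 / 39.02 / 67.06 |
| 3% | 1,505 | 93.19 / 38.61 / 66.63 |
| 5% (stress case) | 1,575 | 93.03 / 38.37 / 66.36 |

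At 3% no value moves by more than 0.43 points.

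**6. Effect on KPI rates.** Shift = share of the enlarged subset × difference in KPI performance between early deaths and the rest. The difference is also assumed.
- 0.5%: 17.5 / 1,417.5 = 1.2%; × 30 points = 0.4 points
- 3%: 105 / 1,505 = 7.0%; × 30 points = 2.1 points; × 50 points = 3.5 points
- 5% (stress case): 175 / 1,575 = 11.1%; × 30 points = 3.3 points; × 50 points = 5.6 points

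The detectable gains in Table 1 are 93.4 − 85 = 8.4, 39.0 − 27 = 12.0 and 67.1 − 54 = 13.1 points.

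**7. Change in membership between phases.** Illustration only: suppose early mortality fell from 3% to 2% of all patients and those survivors entered the subset. They would form 0.01 / (0.40 + 0.01) = 2.4% of it. A 30-point difference in their KPI performance would move the subset rate by 0.7 points, and a 50-point difference by 1.2.

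**The case against.** - **The rule sits only in the power section.** It is a parenthesis and a table heading introducing examples, and the analysis section does not adopt it. That is true. But the sentence says to whom the additional KPIs apply, and no other rule exists. An analyst would either use it, and lose the early deaths, or have no denominator. Both call for a definition in the analysis section.
- **A reader might infer that these KPIs are never assessed in patients who die early.** The documents do not support that. Observation covers every injured patient as care is given, and nothing makes it depend on a 24-hour rule that could not be applied at first assessment.
- **A reader might infer that the results would describe only survivors and transfers.** That is too broad. Deaths after 24 hours count, as do deaths after referral.
- **The same rule holds in both phases, so the TIF effect need not be distorted.** This stands. Differential membership is possible but not demonstrated, and the illustration above is small.
- **Very early deaths may leave too little time for some KPIs**, so counting them as failures could misstate appropriate use. This also stands. It is a reason to show results both ways, not to leave the group out without saying so.

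**Conclusion.** The point holds as a gap in the analysis-set definition. Followed as written, the plan excludes unreferred patients who die in the emergency unit or before 24 hours from the serious-injury KPIs, although their care is observed and their deaths are recorded.

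Under an assumed early mortality of 0.5% to 3%, the exclusion is 18 to 105 patients, or 1.3% to 7.5% of 1,400. With a further assumed 30-point difference in KPI performance, the subset rates would shift by about 0.4 to 2.1 points. Power is practically unaffected, and the claim "we have 80% power to detect (at a minimum) the post-TIF values indicated" is not called into question here. Bias in the before-and-after comparison is not shown. The loss is small on average but complete for unreferred early deaths, a group at the centre of Aim 1. It is a cheap improvement worth making and does not threaten the trial's main result.

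**What to change.** In the Specific aim 1 sample size text, the Table 1 heading and Statistical Analyses for Specific Aims 1 and 2, define the serious-injury analysis set as patients who were referred out, were admitted for at least 24 hours, or died in the emergency unit or before 24 hours. Exclude those dead on arrival, in whom no assessment was possible. State that the same definition applies before and after TIF introduction, and report each serious-injury KPI with and without the early deaths.

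The cost is one definition repeated in three places and one extra display. No new data are needed. The subset grows slightly, and Table 1 barely changes. The small downside is that very early deaths may allow little time for some KPIs, and the paired display makes this visible.

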IMPROVING INITIAL MANAGEMENT OF THE INJURED AT GHANAIAN DISTRICT AND REGIONAL HOSPITALS WITH A TRAUMA INTAKE FORM

- Protocol and Statistical Analysis Plan

NCT #: **NCT04547192**

Date: **December 3, 2019**

STUDY PROTOCOL

We propose a pragmatic randomized clinical trial to be carried out at 8 district and regional hospitals in Ghana. The intervention to be tested is the Trauma Intake Form (TIF) to be used in recording information about injured patients during their initial assessment and care and which is designed to serve as a memory prompt (built-in checklist) to decrease omission of critical steps in care and so to improve care and to improve record keeping. The unit of randomization will be hospitals and a stepped-wedge design will be used to select which hospitals will start use of the TIF at what time.

Overall Strategy and Methods.

Methods for specific aims 1 and 2.

Specific aim 1. *To determine the effectiveness of a model Trauma Intake Form (TIF) to function as a checklist for increasing the appropriate use of key performance indicators (KPIs) (e.g. airway maintenance, tests to exclude internal bleeding, examination of distal pulses, pulse oximeter placed) during care of the injured in emergency units in district and regional hospitals in Ghana, as assessed by independent observers.*

Specific aim 2. *To determine the percent of injured patients with adequate data on initial assessment before vs. after introduction of the TIF in emergency units in district and regional hospitals in Ghana.*

The effectiveness of the TIF will be assessed at the 8 study hospitals by measuring the use of KPIs during initial care of the injured before vs. after introduction of the TIF. Data on the KPIs will be obtained from *observations* by research assistants (RAs) of care provided by EHSPs and by *data from medical records*.

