Specific Aim 2: The above patient numbers, alpha and power levels, and COV range apply. We are powered to detect an increase in the documentation of important clinical data (including *all* of: time of injury, mechanism of injury, respiratory rate, heart rate, blood pressure, consciousness level, temperature, and time of disposition) by at least 5% (10% to 15%).

Statistical Analyses for Specific Aims 1 and 2

We will perform descriptive statistics (e.g. percents, means) to describe characteristics of injured patients, including age, gender, mechanism of injury and initial diagnosis. For Spec Aim 1, we will create binary variables describing whether each of the KPIs of care (as specified by the TIF) were performed. Similarly, for Spec Aim 2, we will create a binary variable describing whether adequate data (*all* of the following: time of injury, mechanism of injury, respiratory rate, heart rate, blood pressure, consciousness level, temperature, and time of disposition) have been recorded for each patient. Differences in performance of KPIs or adequate data recorded will be estimated using generalized linear mixed models, adjusted for TIF introduction and time periods as fixed effects and hospitals and time periods as random effects. We will use STATA version 17 (College Station, TX) for all analyses. Data will be analyzed on an intention-to-treat basis.

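### Eight hospitals, no small-sample method: the z test can be too liberal if hospitals vary from period to period, and Table 1's 80% power is overstated under a small-sample reference

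*Combined protocol and SAP*

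**What the plan says.** The introductory protocol text states: "We propose a pragmatic randomized clinical trial to be carried out at 8 district and regional hospitals in Ghana". Under the methods for introducing the TIF, the rollout is staggered across those hospitals, and "We will consider two nearby hospitals as a group, thereby getting four groups of hospitals". Each step lasts 14 weeks, and "The total duration of observation of EHSP practices will be 70 weeks". That makes five periods and 8 × 5 = 40 hospital-periods.

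Under Sample size calculations, Specific aim 1, the plan expects "over the 17.5 months recruitment period at the 8 sites, a total of 3,500 patients" and claims that "we have 80% power to detect (at a minimum) the post-TIF values indicated", at alpha 0.05 and a coefficient of variation (COV) of 0.25, with a range of 0.15 to 0.40. For the subset with additional KPIs, "we anticipate 40% (n=1,400) of patients will be seriously injured".

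Under Statistical Analyses for Specific Aims 1 and 2, differences "will be estimated using generalized linear mixed models". TIF and period are fixed terms, hospitals and periods are random terms, and the software is Stata 17. Neither the analysis nor the sample-size text mentions a degrees-of-freedom method, a t reference, a restricted-likelihood fit, a permutation test or any other allowance for eight clusters. The power formula and its quantiles are not named either.

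**The concern.** With eight hospitals, likelihood estimates of the hospital and hospital-period variances tend to be too small, and a z reference ignores the uncertainty in them. Standard errors then come out too small and the test too liberal, even when the random terms are the right ones. This is a separate matter from which random terms to include. If the power calculation also uses normal quantiles, it treats the degrees of freedom as unlimited. At stake are confidence intervals and p-values for every KPI in Aim 1 and for the documentation outcome in Aim 2, and the credibility of the 80% in Table 1.

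**Working it through.** **Inputs from the documents.** I = 8 hospitals; four pairs crossing over one step apart; T = 5 periods (70/14). Patients per hospital-period: 3,500/40 = 87.5 for all injured, 1,400/40 = 35 for seriously injured. COV 0.25, alpha 0.05 (taken as two-sided), power 80%, and the Table 1 rates. **Assumed:** any hospital-by-period variance.

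**Reproducing Table 1.** The Hussey-Hughes variance is

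Var = Iσ²(σ² + Tτ²) / [(IU − W)σ² + (U² + ITU − TW − IV)τ²],

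with σ² = p̄(1 − p̄)/n, p̄ the mean of the two rates, and τ = COV × baseline. For this design U = 20, W = 120 and V = 60, so the bracket is 40σ² + 120τ².

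Internal bleeding: σ² = 0.33 × 0.67/35 = 0.00632; τ² = (0.25 × 0.27)² = 0.00456; SE = 0.0429. Then 0.12/0.0429 = 2.80 and power = Φ(2.80 − 1.96) = 80%. All six detectable values at COV 0.25 match to one decimal with 1.96 + 0.84 (table below). The low-COV ends of the ranges match only to within 0.3 points.

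**Power under a small-sample reference, no hospital-by-period variation.** Regressing the 40 proportions on hospital, period and TIF leaves 40 − 8 − 4 − 1 = 27 residual degrees of freedom. Fixed hospital effects correspond to τ² → ∞ above, so Var = 40σ²/120 = σ²/3. Power is from the noncentral t, with critical value 2.052.

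| Row | Table 1 | Formula with 1.96 + 0.84 | Regression SE | Difference/SE | Power, t(27) | Detectable at 80% |
|---|---|---|---|---|---|---|
| Blood pressure | 77.6 | 77.57 | 0.0271 | 2.80 | 77% | 77.9 |
| Heart rate | 68.2 | 68.23 | 0.0296 | 2.77 | 76% | 68.6 |
| Consciousness | 58.5 | 58.52 | 0.0307 | 2.76 | 76% | 58.9 |
| Chest | 93.4 | 93.44 | 0.0303 | 2.77 | 76% | 93.7 |
| Internal bleeding | 39.0 | 39.02 | 0.0459 | 2.61 | 71% | 40.4 |
| Distal pulses | 67.1 | 67.06 | 0.0477 | 2.75 | 75% | 67.8 |

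Keeping the mixed-model SE and using t on 6 degrees of freedom (hospitals minus 2) gives 64% to 65% in every row.

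**Power with hospital-by-period variation.** A logit SD of s adds about (s·p̄(1 − p̄))² to σ². At s = 0.2:
- Blood pressure: 0.00221 + 0.00150 = 0.00371; SE = √(0.00371/3) = 0.0351; 0.076/0.0351 = 2.16; power 55%.
- Internal bleeding: 0.00632 + 0.00196 = 0.00827; SE = 0.0525; 0.12/0.0525 = 2.29; power 60%.

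At s = 0.4 the figures are about 29% and 39%.

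**Size of the z test under no effect.** Binomial logit models were fitted by maximum likelihood (Laplace) with hospital and hospital-by-period effects, matching how the data were generated. The hospital logit SD implied by COV 0.25 is COV/(1 − baseline): 0.50 for consciousness, 0.83 for blood pressure, 0.34 for bleeding. A period-specific share f gives a logit SD of √f times that.

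| Scenario | Hospital-by-period logit SD | Replicates | z rejects |
|---|---|---|---|
| Consciousness | 0 | 1,500 | 5.3% |
| Internal bleeding | 0 | 1,500 | 6.1% |
| Consciousness, f = 10% | 0.16 | 1,500 | 8.8% |
| Consciousness, f = 20% | 0.22 | 1,500 | 7.8% |
| Blood pressure, f = 10% | 0.26 | 1,500 | 8.2% |
| Internal bleeding, f = 20% | 0.15 | 1,500 | 7.0% |
| Blood pressure | 0.2; 0.4 | 500 each | 8.8%; 8.2% |
| Internal bleeding | 0.2; 0.4 | 500 each | 8.6%; 7.8% |

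In the 500-replicate runs the mean SE was 0.89 to 0.93 of the empirical SD, so 7% to 11% too small. A linear mixed model on cell means (10,000 replicates per setting) gave 4.9% with no such variation and 8.0% to 9.5% with it. With a restricted-likelihood fit, z gave 6.0% to 7.1% and t on 26 degrees of freedom about 5% to 5.7%.

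**Size of the regression test.** Over 20,000 replicates per scenario (baselines 70% and 27%; logit SD 0, 0.2, 0.4), t(27) rejected 4.7% to 5.2%.

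**The case against.** The strongest reply is that the inflation rests on a variance the documents do not give. Without it the z test is close to nominal. The upper end of the assumed range is also generous for some rows: an SD of 0.4 exceeds the 0.34 between-hospital SD implied for internal bleeding. Both points stand, so a reader who infers that the 5% test does run at 8% to 9% goes further than the documents allow. What remains is that the plan itself lists periods among the random terms and observes for 70 weeks, so such variation cannot be ruled out, and a prespecified test should hold its size if it is there.

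Second, the plan says neither maximum likelihood nor z, and does not say whether random periods are nested in hospitals. That is correct: the simulations take the large-sample default and one reading of the random terms. But leaving the reference distribution open until the data are seen is what an analysis plan should prevent.

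Third, simulation precision is limited. At 500 replicates the exact 95% interval for 7.8% is 5.6% to 10.5%. At 1,500 the interval for 7.0% is 7.0 ± 1.96 × √(0.07 × 0.93/1,500), or 5.7% to 8.3%, still above 5%.

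Fourth, t(27) is not valid in every setting. With a TIF effect that varies between hospitals (assumed logit SD 0.4, mean zero), it rejected 7.9% for blood pressure and 6.4% for bleeding. This stands, and is why the fix adds a permutation check.

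**Conclusion.** The concern holds in conditional form. The plan names no small-sample method for eight hospitals. If hospital-by-period variation is present (assumed logit SD about 0.15 to 0.4), a maximum-likelihood z test rejects about 7% to 9% instead of 5%; if it is absent, about 5% to 6%.

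The 80% power is overstated under each small-sample reference tried, by an amount that depends on the reference: 71% to 77% by row for the hospital-period regression with t(27), and 64% to 65% for the mixed-model SE with 6 degrees of freedom, both with no hospital-by-period variation. With such variation, power is much lower. That Table 1 uses normal quantiles is inferred from the match in all six rows, not stated.

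A reader might infer a uniform loss of about 3 points, to 77%, by putting t(27) into the Table 1 formula. That pairs the mixed-model SE, which uses between-hospital information, with the degrees of freedom of a regression that discards it. It understates the loss, most clearly for internal bleeding (71%, detectable value 40.4). It also assumes away the variation that produces the size inflation. Nor does the point show that the design fails or that the trial must be enlarged.

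**What to change.** In the statistical analyses section, prespecify one small-sample-valid test for the TIF term. One choice is to regress the 40 hospital-period proportions on hospital, period and TIF, with t on 27 degrees of freedom. This gives a percentage-point difference, the scale of Table 1. Add a permutation test over the randomised order as a check. If the four pairs are the randomised units there are 4! = 24 orders, so its p-value cannot fall below 1/24 = 0.042, which limits it to a supporting role. Keep the patient-level mixed model for adjusted estimates, and state whether its random periods are nested in hospitals.

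Restate Table 1, as power or as detectable values, using the SE and degrees of freedom of the chosen test, with a stated range for hospital-by-period variation.

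The cost is plan wording, one extra regression on data already being collected, slightly wider intervals and a less favourable stated power. No extra patients or hospitals are needed.
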